## 5.2. Subject Exclusion Criteria

Subjects will be excluded for any of the following conditions/reasons:

1. Women who are pregnant or lactating or have a positive serum pregnancy test at enrollment or positive urine pregnancy test at any time during the study.
2. Smokers. A “smoker”, for the purposes of the study, will be defined as an individual who has regularly and habitually used nicotine-containing substances, including tobacco products (e.g., cigarettes, cigars, chewing tobacco, gum, patch or electronic cigarettes) over the past 12 months. Occasional recreational use (less than once monthly) will not warrant exclusion unless the individual has used nicotine-containing substances in the previous 30 days before study enrollment.
3. Participation in any ongoing investigational drug trial or clinical drug trial period unless the study is in the follow-up phase and it has been  $\geq$  one month since the subject received any experimental agents or treatments.
4. Abnormal vital signs, defined as:
  - Hypertension (systolic blood pressure  $\geq$ 140 mmHg or diastolic blood pressure  $\geq$ 90 mmHg) at rest on two separate days.
  - Heart rate  $<55$  at rest on two separate days
  - Respiratory rate  $\leq 11$  to  $\geq 18$  breaths per minute
5. Temperature  $>38.0^{\circ}\text{C}$  ( $100.4^{\circ}\text{F}$ ) or symptoms of an acute self-limited illness such as an upper respiratory infection or gastroenteritis within seven days of administration of a study product.
6. History of chronic obstructive pulmonary disease.
7. Positive urine drug screening test.
8. Use of any prescription medication during the period 0 to 30 days or over-the counter medication during the period 0 to 3 days before entry to the study (vitamins, herbal supplements and birth control medications will be allowed).
9. Use of medications or treatments that would significantly influence or exaggerate responses to the test product or that would alter inflammatory or immune response to the product. This includes antihistamines (within 72 hours prior to dosing), systemic or topical corticosteroids within four weeks prior to dosing, use of monoamine oxidase inhibitors 21 days prior to study, cyclosporine, tacrolimus, cytotoxic drugs, immune globulin, Bacillus Calmette-Guerin [BCG], monoclonal antibodies, or radiation therapy.
10. Donation or loss of greater than one pint of blood within 60 days of entry to the study.
11. Any prior serious adverse reaction or hypersensitivity to lidocaine administered by any route.
12. Current diagnosis of any major psychiatric illness.
13. Received an experimental agent (vaccine, drug, biologic, device, blood product or medication) within 30 days before enrollment in this study or expects to receive an experimental agent during the study.

14. Medical history of a serious chronic condition, including (but not limited to): allergic conditions such as anaphylaxis to food or drugs; asthma; generalized drug reactions; any seizure disorder; any central nervous system disorder; glaucoma (open or closed angle); history of pyloric or urinary bladder neck obstruction; intestinal obstruction; difficulty swallowing; stomach or bowel problems (e.g. blockage, muscle weakness, ulcerative colitis, Crohn's disease); bleeding disorders; acid reflux disease; myasthenia gravis; allergy to belladonna alkaloids; impaired hepatic or renal function.
15. Any condition that would, in the opinion of the Principal Investigator (PI) or MAI, place the subject at an unacceptable risk of injury or render the subject unable to meet the requirements of the protocol.
16. Inability to communicate or cooperate with the investigators.
17. Medical history of significant dermatologic diseases or conditions, such as atopy, psoriasis, vitiligo or conditions known to alter skin appearance or physiologic response (e.g. diabetes, porphyria).
18. History of significant dermatologic cancers (e.g. melanoma, squamous cell carcinoma), except basal cell carcinomas that were superficial and did not involve the investigative site.
19. History of consumption of alcohol within 24 hours prior to dose administration.
20. Subject has an obvious difference in skin color at patch sites (compared to neighboring skin), or the presence of a skin condition, excessive hair at the application site, sunburn, raised moles and scars, open sores at application site, scar tissue, tattoo, or coloration that would interfere with placement of test articles, or the assessment of the skin and/or reactions to drug.

### **5.3. Enrollment Procedures**

#### **5.3.1. Randomization Procedures**

When found eligible to participate, the subject will be enrolled in one of the two study groups. The group assignment will be assigned based on alternating Group 1 or 2 for every other subject.

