### 2.2. Rationale

The rationale of this study is to determine the absolute bioavailability and pharmacokinetics of topical lidocaine through development of an appropriately controlled and well-characterized methodology to quantify the exposure of healthy adults to lidocaine during wear, so that the rate of drug release and delivery can be defined in a manner that can help the regulatory agency (FDA) in developing Guidances for Industry regarding the characterization of drug release and absorption kinetics to ensure the safety of individuals utilizing these types of products.

The project involves crossover pharmacokinetic (PK) studies using two lidocaine topical patch products made by different manufacturers, and IV injection of the corresponding drug (e.g. lidocaine hydrochloride). The IV data will be utilized to determine clearance (CL) of the drug from the systemic circulation. Different mathematical approaches including, but not limited to, deconvolution will then be utilized to determine the rate of drug delivery from the patch into the systemic circulation using PK parameters derived from non-compartmental and/or compartmental analyses of lidocaine serum concentrations measured using sensitive, validated bioanalytical methods. In order to compare the data obtained from this study to previously published data, a similar time course was selected for collecting the blood samples for serum analysis. As part of this study, appropriate methodologies will also be developed to precisely characterize the (residual) drug content in the selected products. Following the *in vivo* studies, residual drug content of the worn patches will be determined to calculate exposure from the patch (i.e. quantifying the amount of drug delivered *in vivo* over time based upon residual drug analysis data).

Since this will be a crossover study, all subjects will complete all three study arms. One of the patch systems will be applied first, followed by at least 48 hours of washout period. Then the IV injection will be administered followed by at least 48 hours of washout period. Last, the second patch system will be applied. Subjects will be assigned to one of two groups. Regardless of group, all subjects will receive the treatments in the same order of patch-IV-patch. In Group 1 the patch manufactured by Mylan will be applied first; in Group 2 the patch manufactured by Endo Pharmaceuticals will be applied first.

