The half-life of topical lidocaine after patch removal is approximately 6 – 8 hours. Hence, 48 hours (i.e. ~5 to 6 half-lives) will be sufficient for >95% of lidocaine to be eliminated from the body after topical administration. The half-life after IV administration is approximately 1.5 – 2 hours. Ten hours of sampling will be sufficient for >95% of lidocaine to be eliminated from the body. Each subject will be enrolled to complete all study arms and procedure days. The study is open-label and not blinded because PK assessment is not subject to participant and/or observer bias. After each study arm is completed, the available safety data will be reviewed by an Independent Safety Monitor (ISM) to determine whether or not the subject will proceed to the next study arm.

A schedule of events is provided in **Appendix A**.

This study will be conducted in the CRU outpatient unit of the Institute for Clinical and Translational Science (ICTS) in the University of Iowa Hospitals and Clinics (UIHC). Conducting studies in this well-prepared research-oriented unit ensures that each subject is carefully observed throughout the study. If any adverse events occur, they can be properly documented and the subjects provided with the appropriate care. The CRU is a fully equipped research unit in UIHC, with inpatient and outpatient facilities, nursing staff on site and the MAI is available on- or offsite via the hospital pager system. The hospital code team is available to manage any unanticipated life-threatening emergency, and less urgent issues will be managed by the MAI.

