#### **5.3.6. Subject Discontinuations**

The term "discontinuation" refers to a subject's non-completion of a study whether by their own choice, the PI/MAI/ISM's decision, or due to discontinuation of the study by the Sponsor. Subjects who discontinue prematurely after administration of the patch or IV injection will be replaced and their PK samples will be analyzed. Alternates will be recruited in the event study subjects are unavailable at the time of check in at the outpatient unit (CRU) or at any of the procedure days. It is expected that at least ten alternates will be recruited. An adequate number of alternates will be screened to ensure any dropouts can be replaced until a total of 24 subjects complete all study procedures.

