### 7.3. Study Visits and Procedures

#### Pivotal study (n = 24 subjects)

Since this is a crossover study, subjects will be divided into two groups (n = 12/group). The only difference between groups is the order in which they go through the study arms. There will be a minimum 48 hour washout period between study arms.

Group 1	Group 2
Study arm 1: Lidocaine 5% patches (Mylan) Study arm 2: Lidocaine injection Study arm 3: Lidoderm® 5% patches	Study arm 1: Lidoderm® 5% patches Study arm 2: Lidocaine injection Study arm 3: Lidocaine 5% patches (Mylan)

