### 10.4. Statistical Analysis Plan

Primary statistical analysis will be performed on the natural log transformed  $AUC_{0-t}$ ,  $AUC_{0-\infty}$  and  $C_{max}$  of lidocaine from the two treatments. The following will be obtained:

- A linear mixed effects model will be used to assess the effects of treatment, period, sequence, and subject within sequence on the natural log transformed  $AUC_{0-t}$ ,  $AUC_{0-\infty}$  and  $C_{max}$  of lidocaine. For this, the treatment, period, and sequence effect will be treated as fixed effects (assessed at a significance level of 0.05) while the subject within sequence will be treated as a random effect.
- Intra- and inter-individual variabilities will be obtained.
- The least squares mean estimates for the adjusted differences between treatment means (the log transformed  $AUC_{0-t}$ ,  $AUC_{0-\infty}$  and  $C_{max}$ ) and the standard error associated with these differences will be obtained.
- The 95% confidence intervals for absolute bioavailability of the lidocaine patches will be obtained.

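### Sequence groups are assigned by alternation under a randomization heading, which leaves the Mylan/Lidoderm ratio open to a bias that is probably small; a concealed random list avoids this at no cost in subjects

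*Combined protocol and SAP*

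**What the plan says.** Section 5.3.1, under the title "Randomization Procedures", contains two sentences. The first is "When found eligible to participate, the subject will be enrolled in one of the two study groups"; the second is "The group assignment will be assigned based on alternating Group 1 or 2 for every other subject". No starting group is named, and nobody is named as the assigner. No section mentions a generated list, a seed, blocks or concealment. Section 5.3.2 says that masking does not apply, and Section 4 explains why: "The study is open-label and not blinded because PK assessment is not subject to participant and/or observer bias".

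Section 2.2 sets the order: "Regardless of group, all subjects will receive the treatments in the same order of patch-IV-patch". The groups differ only in which patch comes first. Section 7.3 gives the planned split: "subjects will be divided into two groups (n = 12/group".

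On dropouts, Section 5.3.6 provides for alternates so that "dropouts can be replaced until a total of 24 subjects complete all study procedures". It does not say which group a replacement joins.

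Section 10.3 sizes the study on a test-versus-reference formulation difference. Section 10.4 fits a mixed model in which "the treatment, period, and sequence effect will be treated as fixed effects", each assessed at 0.05.

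**The concern.** Alternation is systematic. Anyone who knows the last assignment knows the next one before the next volunteer is judged eligible. Staff have ordinary discretion over who enters and when: Section 7.1 allows abnormal laboratory values to be repeated, exclusion 15 in Section 5.2 rests on investigator opinion, and Section 5.3.6 lets alternates step in. The reason given in Section 4 for an open-label design concerns measurement. It does not address who enters which sequence.

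At stake is the contrast between the two patches. In a two-sequence crossover it is estimated by comparing the two groups' within-subject differences. With random allocation, the groups can differ in period change only by chance, and the standard error covers that. With alternation, the same analysis rests on an assumption that the groups are exchangeable.

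**Working it through.** **1. The plan's own figure.** Section 10.3 gives N = 24, 22% within-subject variability, 80% power, a 5% formulation difference and 5% type I error. It states no equivalence limits, so 0.80 to 1.25 is an assumption here.

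- σ_w = √ln(1 + 0.22²) = 0.217
- SE of the log patch ratio = 0.217 × √(2/24) = 0.063
- Two one-sided tests at 0.05, true ratio 0.95: smallest even N is 22 (power 80.4%); N = 24 gives 83.8%.

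Under those limits, 24 is reproduced to within two subjects. Changing the allocation method does not change N.

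**2. Predictability.** With 24 subjects, 23 assignments follow the first and all 23 are determined by it. The first is uncertain only because the starting group is not stated.

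| Method | Possible lists | Share guessed correctly, best strategy |
|---|---|---|
| Alternation | 1 (start fixed) or 2 (start drawn) | 100% after the first |
| Blocks of 2, size known | 2^12 = 4,096 | 75% |
| Blocks of 4, size known | 6^6 = 46,656 | 71% |
| Random 12:12 list | C(24,12) = 2,704,156 | 61% |

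A randomisation test could reach no p-value below 1.0 (start fixed) or 0.5 (start drawn) under alternation. With a random 12:12 list the minimum is 2/2,704,156 = 7.4 × 10⁻⁷.

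**3. What cancels.** Let D = log(Mylan/Lidoderm), and let δ1 and δ2 be the change in log exposure, apart from product, from the first to the second patch period in Groups 1 and 2.

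- Group 1 (Mylan first): mean of first minus second = D − δ1
- Group 2 (Lidoderm first): mean of first minus second = −D − δ2
- Estimate of D = half the difference = D − (δ1 − δ2)/2

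Each subject's own level drops out of both lines, and a change common to both groups drops out of the estimate. Half of any group difference in change remains.

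For IV, the average of the two patches minus IV is formed within each subject, with IV in period 2 in both groups, so δ1 − δ2 does not enter it. The two single-patch bioavailabilities can move only through the patch ratio. They shift by (δ1 − δ2)/4 in opposite directions if the same fraction of the change has occurred by the IV period in both groups.

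**4. Size.** The documents give no value for the group difference, so these are assumptions:

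- 5%: ln(1.05)/2 = 0.024, a bias of about 2.5%
- 10%: ln(1.10)/2 = 0.048, about 4.9%
- 20%: ln(1.20)/2 = 0.091, about 9.5%

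The 95% half-width is t(22) × SE = 2.074 × 0.0628 = 0.130, which is ×/÷1.14.

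**5. Split among completers.** A 14/10 split changes the variance by (1/14 + 1/10)/(1/12 + 1/12) = 1.029, about 3% more. A simulation continued alternation through all enrolled subjects until 24 completed, with independent dropout at assumed rates. An exact 12:12 split occurred in about 63% of trials at 5% dropout, 49% at 10% and 36% at 20%. A split of 14/10 or worse occurred in about 2%, 6% and 18%.

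**The case against.** The strongest reply is that no plausible mechanism produces the bias. Staff would have to foresee which healthy volunteer's lidocaine exposure would rise or fall between patch periods, and time enrolment accordingly. Nothing in the documents suggests that this can be foreseen or that anyone would gain from it. Every subject receives all three products, the endpoint is a serum assay run at another institution (Sections 8.2.2 and 8.3.1), and alternation in calendar order tends to balance slow time trends. This stands, and it is why the likely bias is small. It does not turn alternation into randomisation.

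The patch-versus-patch ratio is also not a listed objective: Sections 3.1 and 10.1 put absolute bioavailability first. That is correct, but Section 10.3 sizes the study on this contrast and Section 10.4 models it.

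A reader might infer that a group difference in period change would be mixed up with carryover or a true sequence effect. The documents do not support that. Such a difference is aliased with the treatment contrast, while the sequence term comes from subject totals. Carryover is remote: from removal of the first patch to application of the second is at least 36 + 48 + 10 + 48 = 142 h. At the longer 8 h half-life in Section 4 that is about 18 half-lives, leaving about 5 parts per million. Each patch arm also has a pre-dose sample.

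A reader might also infer that the study is presented throughout as randomised. It is not: the Protocol Summary and Section 4 call it a three-arm open-label crossover, and only the section title says otherwise.

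**Conclusion.** The point holds in limited form. The heading names a procedure that the plan does not contain, every assignment after the first is predictable, and nothing conceals it. The exposed quantity is the Mylan/Lidoderm ratio, by half of any group difference in period change. Its size cannot be estimated from the documents. It is probably small, and the range of 2.5% to 9.5% rests entirely on assumed differences of 5% to 20%. The ×/÷1.14 limits rest on the 22% variability in Section 10.3 and 24 completers split 12:12.

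It would go too far to conclude that the absolute bioavailability results are invalid. The overall patch-versus-IV comparison does not compare the groups, and a random sequence list would not alter the fact that IV always falls in period 2. Nor do the documents show that the person enrolling subjects makes or sees the assignments; they only leave this open.

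The missing replacement rule is minor, given the 3% variance cost of a 14/10 split. The change is worth making because it costs almost nothing.

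**What to change.** Replace the alternation sentence in Section 5.3.1 with a computer-generated permuted-block list:

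- varied block sizes that are not disclosed to the study team, 12 per sequence;
- prepared by someone outside enrolment;
- held by the pharmacy, which already dispenses product for each arm (Section 6.6);
- each assignment released only after eligibility is confirmed.

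Undisclosed, varied sizes matter, because blocks of a known size of 2 or 4 can still be guessed 75% or 71% of the time.

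State what happens to replacements. A replacement may take the sequence of the subject replaced, which keeps 12:12 among completers. The downside is that this assignment is known beforehand, so it is a measure for balance only, and the gain is small. Otherwise, extend the list to cover the alternates (24 + 10 = 34 places) and accept a slightly uneven split.

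If alternation is kept, rename the section and describe the allocation as non-random in the protocol and the report.

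The cost is one paragraph of protocol text and a short list. N stays at 24, with no added visits or procedures.

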#### **5.3.2. Masking Procedures**

Not applicable.

#### **5.3.3. Reasons for Withdrawal**

The primary reason for a subject's discontinuation should be selected from the following standard categories:

***Adverse Event (AE)*** – Clinical or laboratory events that in the judgment of the PI or MAI require discontinuation from the study in the best interest of subject. All AEs must have their relationship to the patch or IV injection assessed using the following terms: Associated or Not Associated. Upon occurrence of a Serious Adverse Event (SAE) possibly requiring discontinuation of a subject, the PI will confer with the ISM. If a subject is discontinued due to an AE, the event will be followed until it is adequately resolved.

#### ***Death***

***Protocol Deviation*** – The subject's findings or conduct failed to meet the protocol entry criteria or failed to adhere to the protocol requirements. The violation necessitated premature termination from the study as determined by the PI or MAI in consultation with the ISM.

**Withdrawal of Consent** – Subject desires to withdraw from further participation in the study in the absence of a medical need to withdraw as determined by the MAI. Subjects are free to withdraw from participating in the study at any time upon request.

#### **Pregnancy**

**Other** – Causes of premature termination from the study other than the above, such as suspension or termination of study, study site, or at investigator or Sponsor discretion.

#### **5.3.4. Screen Failures**

Subjects who signed an informed consent form and have undergone screening procedures, but who do not meet all entry criteria, will be considered screen failures and will not be enrolled. The reasons for screen failure will be documented. A screen failure also includes a screened subject who meets eligibility criteria but decides not to participate in the study.

#### **5.3.5. Termination of Study**

In the event that the study is discontinued, subjects will not progress on to the next procedure day. Enrolled subjects who have completed any procedure day will be followed for resolution of any ongoing AEs and will be contacted to evaluate the occurrence of any new AEs within 48 hours of the last procedure day completed.

#### **5.3.6. Subject Discontinuations**

The term "discontinuation" refers to a subject's non-completion of a study whether by their own choice, the PI/MAI/ISM's decision, or due to discontinuation of the study by the Sponsor. Subjects who discontinue prematurely after administration of the patch or IV injection will be replaced and their PK samples will be analyzed. Alternates will be recruited in the event study subjects are unavailable at the time of check in at the outpatient unit (CRU) or at any of the procedure days. It is expected that at least ten alternates will be recruited. An adequate number of alternates will be screened to ensure any dropouts can be replaced until a total of 24 subjects complete all study procedures.

#### **5.3.7. Handling of Withdrawals**

When handling withdrawals, every effort will be made to undertake protocol-specified safety follow-up procedures. However, should the subject decide to withdraw, the primary reason for withdrawal shall be recorded by a study team member in the subject's data collection form. Written withdrawal will be requested if the subject decides to withdraw by his or her own choice. The study team will attempt to collect safety data on any subject who leaves the study. If voluntary withdrawal occurs due to an AE, the subject will be asked to continue scheduled evaluations and be given appropriate care under medical supervision until the symptoms of any AE resolve or for 48 hours after completion of any study arm. Subjects who fail to return for the second or third procedure day or arm of the crossover study will be contacted by the site in an attempt to have them comply with the protocol. At a minimum, two phone calls and a certified, return receipt letter should be employed in an attempt to contact every subject who discontinues prematurely due to an AE.

